Study Protocol and Statistical Analysis Plan

Musical Grammatological and Neurocognitive Parameterization of Analgesic and Anxiolytic
Effects of Culturally and Personally Contextualized Music Listening During Painful Dental
Procedures

16/07/2025

Musical Grammatological and Neurocognitive Parameterization of Analgesic and Anxiolytic Effects of Culturally and Personally Contextualized Music Listening During Painful Dental Procedures

I-Objective

This study aims to verify, with a significant sample of 30 Lebanese adults, the hypothesis that listening to a personally and culturally contextualized musical sequence during a painful dental procedure induces a significant decrease in perceived pain and patient anxiety. The music is chosen by the patient from a pre-established selection of tracks based on grammatological criteria recognized for their analgesic potential. The study also seeks to observe favorable modulation of physiological parameters related to stress.

II- Research Questions

- Can listening to a musical statement chosen from a pre-selected palette based on soothing musical grammatological criteria induce an analgesic effect in patients undergoing painful dental care?
- Would this musical statement have a modulating effect on the activity of the autonomic nervous system, particularly by inhibiting physiological responses associated with stress?
- Do the analgesic and anxiolytic effects of the musical sequence vary according to implicit cultural preferences (e.g., Mashriq musical tradition vs. Western music) expressed in the patient's choice?
- Are the musical sequences chosen freely by patients from a pre-established palette perceived as effective in mitigating pain and anxiety, and to what extent is this perception correlated with physiological data and self-assessments?

III- Musical Material

The patient is invited to choose a musical sequence from a palette of tracks from various musical genres, pre-selected for their relaxing and soothing musical grammatological criteria:

- Samā'ī in Rāst mode – Ghassan Sahhab
- Taḥmīlat Rāst – Album *Waṣalāt* – Nidaa Abou Mrad and the Antonine University Classical Arabic Music Ensemble
- Bašraf Rāst – Album *Waṣalāt* – Nidaa Abou Mrad and the Antonine University Classical Arabic Music Ensemble
- Bašraf Rāst – Album *Mikha'il Mashâqa* – Nidaa Abou Mrad and the Antonine University Classical Arabic Music Ensemble
- Taqṣīm in Rāst mode – Ghassan Sahhab
- "In a Sentimental Mood" in D Major – Duke Ellington
- Nocturne Op.9 No.2 in Eb Major – Chopin
- Cello Suite No. 1 in G Major, BWV 1007: I. Prélude in C Major – Bach

- Sonata for Two Pianos K.448: II. Andante in D Major – Mozart
- Clair de Lune in Db Major – Debussy

IV- Type of Dental Procedure Studied

The experimental situation selected for this study is dental drilling during cavity treatment, performed without local anesthesia or in conditions where pharmacological analgesia is partially or totally ineffective.

- **Stimulus:** Dental drilling constitutes a continuous painful stimulus associated with the activation of pain responses and the autonomic nervous system.
- **Scientific Model:** It represents a relevant model for studying central mechanisms of pain modulation (Melzack & Wall, 1965b; Tracey & Mantyh, 2007).
- **Clinical Relevance:** While local anesthesia is standard, it can be ineffective during acute pulp inflammation, in patients with hypersensitivity/intolerance to anesthetics, or due to complex nerve anatomy (Hargreaves & Keiser, 2002; Meechan, 2005).
- **Patient Preference:** Some patients prefer to tolerate the pain of drilling rather than experience the prolonged jaw numbness associated with local injections.
- **Alternative:** In these situations, functional music therapy serves as a pertinent non-drug analgesic alternative. Music is a non-invasive intervention that can modulate perceived pain, anxiety, and autonomic activation through attentional, emotional, and autonomous mechanisms (Bradt et al., 2013; Roy et al., 2008).

V- Methodology

The study was conducted from October 1, 2025, to December 23, 2025, in a private dental clinic in Aley, Mount Lebanon, following ethical approval from Antonine University on July 16, 2025.

V-1- Population

- **Inclusion Criteria:** Adult patients (ages 18–60) visiting the clinic for cavity treatment who provide informed consent.
- **Exclusion Criteria:** Non-consenting patients, children, patients with mental or physical disorders, pregnant women, and patients taking analgesics, anxiolytics, or antidepressants.

V-2- Study Procedure

1. **Welcome:** The patient is welcomed in a calm atmosphere and the procedure is explained.
2. **Assessment:** The patient completes a general information questionnaire and the Corah Dental Anxiety Scale (DAS).

3. **Consent & Selection:** The patient signs the informed consent form, chooses their musical sequence, and adjusts the volume.

On the dental chair :

4. **Baseline (Phase 0):** Heart rate (HR) and blood pressure (BP) are measured at rest (T0).
5. **Control 1 (Phase 1):** 30 seconds of drilling without music. Measurements: HR, BP, and Pain Intensity (PI) via Visual Analog Scale (T1).
6. **Pause/rest (120s) + beginning of the music listening**
7. **Test (Phase 2):** 30 seconds of drilling *during* music playback. Measurements: HR, BP, and PI (T2).
8. **End of the music listening - Pause/rest (120s)**
9. **Control 2 (Phase 3):** 30 seconds of drilling. Measurements: HR, BP, and PI (T3).
10. **Completion:** The patient completes a post-treatment evaluation questionnaire. Note: The study takes place at the start of the clinical visit; dental treatment continues normally after the final study measurements are taken.

VI- Statistical Analysis Plan (SAP)

VI-1 Study Design

- **Type:** Single-arm, within-subject experimental study.
- **Participants:** 30 adults undergoing dental treatment for caries.
- **Phases:** Baseline (T0), Phase 1 (pre-music silence), Phase 2 (music), Phase 3 (post-music silence).
- Each participant serves as their own control.

VI-2- Data Collection: Pain measured via Visual Analog Scale (VAS); heart rate (HR) and systolic/diastolic blood pressure (BP) recorded at all phases.

VI-3- Statistical Methods

Primary Outcome – Pain (VAS)

- **Analysis:**
 - Compare pain levels across phases using repeated measures ANOVA (or Friedman test if data violate normality).
 - Post-hoc pairwise comparisons between phases (Phase 1 vs Phase 2, Phase 2 vs Phase 3) using Bonferroni adjustment to correct for multiple testing.
- **Assumptions:**
 - Normality of residuals checked with Shapiro-Wilk test.
 - Sphericity checked with Mauchly's test; Greenhouse-Geisser correction applied if violated.

Secondary Outcomes

- **Physiological Parameters (HR, BP)**
- **Analysis:**
 - Repeated measures ANOVA for HR, systolic BP, and diastolic BP across the four phases.
 - Pairwise comparisons with Bonferroni correction.
- **Assumptions:** Same as primary outcome; log transformation applied if data are skewed.
- **Post-Treatment Perception of Music Effectiveness**
- **Analysis:**
 - Frequency distributions and descriptive statistics.
 - Association with pain reduction and physiological changes assessed using Spearman correlation.

VI-4- Software

- Statistical analyses will be performed using Python.

Bibliography

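### The objective claims a decrease in anxiety, but no direct anxiety measure is repeated and the SAP plans no anxiety analysis, so that part of the hypothesis cannot be tested

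*Combined protocol and SAP*

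**What the plan says.** Section I sets out to verify that listening to the chosen music "during a painful dental procedure induces a significant decrease in perceived pain and patient anxiety". The title announces "Analgesic and Anxiolytic Effects of Culturally and Personally Contextualized Music Listening During Painful Dental Procedures". Research question 3 in Section II asks: "Do the analgesic and anxiolytic effects of the musical sequence vary according to implicit cultural preferences". Research question 4 asks whether patients perceive the music as helping with pain and anxiety.

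Section V-2 gives the procedure. Step 2 reads: "The patient completes a general information questionnaire and the Corah Dental Anxiety Scale (DAS". This comes before the music is chosen and before the patient is in the chair. At baseline, "Heart rate (HR) and blood pressure (BP) are measured at rest (T0". The first drilling phase lists "Measurements: HR, BP, and Pain Intensity (PI) via Visual Analog Scale (T1" and the music phase "Measurements: HR, BP, and PI (T2"; the last drilling phase (T3) lists the same three items. Step 10 adds a questionnaire after treatment phase 3, without describing its items.

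Section VI-2 summarises data collection as "Pain measured via Visual Analog Scale (VAS); heart rate (HR) and systolic/diastolic blood pressure (BP) recorded at all phases". Section VI-3 makes pain the primary outcome. The secondary outcomes are HR, systolic BP and diastolic BP, and the patient's perception, after the procedure, of how well the music worked. The perception outcome is to be analysed by frequencies, descriptive statistics and Spearman correlation with pain reduction and physiological changes. Neither anxiety nor the DAS is mentioned anywhere in Section VI.

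**The concern.** Anxiety is one of the two effects that the study says it will verify. In a single-arm study where each patient is his or her own comparison, an effect can only be shown as a contrast between phases with and without music. The plan provides that contrast for pain, HR and BP. It does not provide it for anxiety.

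At stake is what the trial may conclude. If the wording stays as it is, a report could state an anxiolytic effect as tested when no planned analysis addresses it. The anxiety part of research question 3, which compares the effect between musical traditions, has the same gap: an effect that is not measured cannot be compared between groups of patients.

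**Working it through.** The plan gives no figure to reproduce. The check sets each measurement point in Section V-2 against the claim, and then does the same for each outcome in Section VI-3.

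| Point in the procedure | Music heard before or during? | Measures listed | Direct anxiety measure |
|---|---|---|---|
| Step 2, before the chair | No | General questionnaire, DAS | 1 |
| T0, rest | No | HR, BP | 0 |
| T1, drilling | No | HR, BP, pain | 0 |
| T2, drilling with music | During | HR, BP, pain | 0 |
| T3, drilling after music | Before | HR, BP, pain | 0 |
| Step 10, end | Before | Questionnaire, items not described | None specified |

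**Step 1: values needed and values available.** A within-person change in anxiety is (anxiety with or after music) minus (anxiety without music), on the same scale. It needs at least 2 comparable values per patient. The procedure specifies 1 + 0 + 0 + 0 + 0 = 1 up to T3, taken before exposure. No change score can be formed for any of the 30 patients.

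**Step 2: planned analyses.** Section VI-3 has three outcome groups: pain, HR/BP, and perceived effectiveness. None is labelled anxiety, and the DAS does not appear as outcome, covariate or subgroup variable.

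**Step 3: can the questionnaire fill the gap?** Research question 4, read with the perception outcome in Section VI-3, suggests that patients may be asked about anxiety relief. Suppose they are. The answer is collected once, after drilling both with and without music, so there is no separate value for each condition. Frequencies and descriptive statistics then describe perceived benefit. A Spearman coefficient depends only on how patients rank relative to one another: it would be the same if every patient's perception score were shifted by the same amount. It therefore says nothing about whether anxiety fell on average.

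**Step 4: can HR and BP fill the gap?** Section I places the stress-related physiological measures in a separate sentence from pain and anxiety, and Section II gives them their own question. Section IV lists anxiety and autonomic activation as different things that music may modulate. It also says that drilling activates both pain responses and the autonomic nervous system. A lower HR or BP at T2 than at T1 could follow from less pain without any change in anxiety. The documents do not define these measures as the anxiety outcome, and on their own account of drilling they cannot serve as one.

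**The case against.** The strongest reply is that post-exposure information on anxiety may exist. A reader might infer from the list of measurements that there are no anxiety data after music at all, or that the questionnaire is a single rating with nothing to compare it with. The documents support neither statement. The items are not described; they could include perceived anxiety relief, or even ask patients to compare drilling with and without music. This part of the objection stands, and the point is limited accordingly. It does not rescue the hypothesis. A comparison recalled at the end is still a perception, and the analyses planned for it are descriptive and correlational.

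A second reply is that pain is the sole primary outcome, measured at T1, T2 and T3 with its own analysis. That is correct. The gap in anxiety does not alter the pain estimate or its test, and it should not be read as a defect in them.

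A third is that nothing in the plan says HR or BP will be presented as anxiety. That also stands: the documents keep them apart, and the plan should not be charged with an intention to substitute one for the other. The relevant point is only that the substitution would not be valid.

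**Conclusion.** The concern holds in this form: no direct anxiety measure is repeated, no analysis of anxiety change is planned, and the DAS is collected but not used in Section VI. One of the two effects in the hypothesis, together with the anxiety part of research question 3, cannot be tested as planned. Descriptive information on perceived anxiety relief may still be available.

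The conclusion rests on two readings. The first is that the procedure lists every scheduled measurement, apart from the unspecified content of the questionnaires. The second is that data collection is over. Section V describes the study in the past tense, with dates from October 1 to December 23, 2025. The cover date of 16/07/2025 and the future tense in Section VI-4 leave some ambiguity. A reader might therefore infer that an anxiety rating could still be added at T1 to T3, but the stated dates do not support that.

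**What to change.** - **Claim.** Remove the statement that the study verifies a decrease in anxiety from the hypothesis in Section I. Remove the anxiolytic part of research question 3, and make no claim of a tested anxiolytic effect in the title or conclusions.
- **Perceived relief.** If the questionnaire asks about anxiety, give the items and report the answers as an exploratory perception outcome, with the descriptive and Spearman analyses already in Section VI-3.
- **HR and BP.** Report them as physiological response only, without interpreting a change as a change in anxiety.
- **DAS.** State in Section VI that it is a baseline measure, used to describe the sample or as an exploratory covariate, and not an outcome.

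The cost is rewording and a narrower stated claim. No new data are needed, and the primary pain analysis does not change.

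### Phases 2 and 3 each follow a 120 s pause but Control 1 has no timed run-in, so the Phase 1 to Phase 2 change in HR and BP can include settling in the chair, and the SAP sets no contrast rule to separate it from music

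*Combined protocol and SAP*

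**What the plan says.** V-2 sets out the sequence on the dental chair:

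- Step 4: "Heart rate (HR) and blood pressure (BP) are measured at rest (T0"). No rest duration, number of readings or stability criterion is given.
- Step 5, Control 1: "30 seconds of drilling without music. Measurements: HR, BP, and Pain Intensity (PI) via Visual Analog Scale (T1"). No interval between T0 and the start of drilling is stated.
- Step 6: "Pause/rest (120s) + beginning of the music listening". Phase 2 drilling follows.
- Step 8: "End of the music listening - Pause/rest (120s"). Phase 3 drilling (Control 2) follows.

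The steps before the chair are untimed. They start with "The patient is welcomed in a calm atmosphere and the procedure is explained" and go on to questionnaires, consent, track choice and volume.

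VI-1 describes a "Single-arm, within-subject experimental study" of "30 adults undergoing dental treatment for caries" and states: "Each participant serves as their own control". The order is fixed: no music, music, no music.

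VI-3 analyses HR, SBP and DBP by repeated measures ANOVA over the four phases, with Bonferroni-corrected pairwise comparisons. It does not name the pairs. For pain it names two: Phase 1 versus Phase 2, and Phase 2 versus Phase 3. There is no time or order term.

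**The concern.** A patient is a clean control for himself or herself only if the compared phases differ in music alone. Phase 1 and Phase 2 also differ in scheduled rest, since T1 is the only drilling measurement without a timed run-in. With one arm and a fixed order, neither randomisation nor a parallel group removes drift with time in the chair.

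If HR and BP are still settling when T1 is taken, T2 will be lower than T1 even if music does nothing. That fall looks the same as the autonomic modulation asked about in II. It would also enter the four-phase ANOVA. It could enter the Spearman correlations in VI-3 too, which use physiological changes without defining them.

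HR and BP are secondary outcomes, but they carry the study's claim about the autonomic nervous system. The point as checked here does not extend to pain.

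**Working it through.** **No figure to reproduce.** The documents give n = 30 but no alpha, power, effect size or SD. What follows illustrates the size of the problem.

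**1. Run-in before each drilling phase (V-2).**

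| Reading | Stated run-in | Music during run-in |
|---|---|---|
| T1 (Control 1) | none timed; follows T0 | no |
| T2 (Test) | 120 s | starts in this step |
| T3 (Control 2) | 120 s | ended |

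**2. Settling model (assumed).** HR above its settled level is A·exp(−t/τ), with no music effect. Assumed A = 2, 5 or 10 bpm, τ = 2, 5 or 10 min, and SD of paired differences 6, 8 or 10 bpm. Readings are placed at the end of each 30 s bout: 0.5, 3.0 and 5.5 min, each gap being 120 s + 30 s = 2.5 min.

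Middle case, A = 5, τ = 5:

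- T1: 5·exp(−0.1) = 4.52
- T2: 5·exp(−0.6) = 2.74
- T3: 5·exp(−1.1) = 1.66
- T1 − T2 = 1.78 bpm, towards music
- T3 − T2 = −1.08 bpm, against music
- (T1 + T3)/2 − T2 = 3.09 − 2.74 = 0.35 bpm

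**3. False-positive rates.** Paired t test, n = 30, noncentrality (bias/SD)·√30. Four phases give 4·3/2 = 6 pairs; with an assumed two-sided 0.05, alpha is 0.05/6 = 0.0083, or 0.4% in the direction of music.

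Middle case with SD 8: noncentrality (1.78/8)·√30 = 1.22, and Phase 1 versus Phase 2 rejects towards music in 6.8% of trials.

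| Quantity, all 27 combinations | Range |
|---|---|
| T1 − T2 bias | 0.4 to 5.6 bpm |
| Phase 1 vs 2 significant towards music | 1% to 98% |
| T3 − T2 bias | −0.3 to −2.2 bpm |
| Phase 2 vs 3 significant towards music | under 0.3% |
| Bias of T2 against the mean of T1 and T3 | 0.05 to 2.0 bpm |

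For the last row, linear drift with equal spacing cancels exactly: T1 and T3 lie the same distance either side of T2.

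**4. Fixed shifts as a cross-check.** With an assumed HR SD of 10 bpm and within-patient correlation 0.70 or 0.85, the SD of differences is 10·√(2(1 − 0.70)) = 7.75 or 10·√(2(1 − 0.85)) = 5.48 bpm. T1 − T2 shifts of 2, 3 and 4 bpm are then significant towards music in 10% to 22%, 26% to 57% and 51% to 87% of trials.

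**5. Effect of a 120 s rest before T0.** Every reading moves 2 min later, so the T1 − T2 bias is multiplied by exp(−2/τ). The reduction is 1 − exp(−2/10) = 18%, 1 − exp(−2/5) = 33% or 1 − exp(−2/2) = 63%. In the middle case 1.78 becomes 1.78·0.670 = 1.19 bpm, and at SD 8 the 6.8% becomes 3.1%. The rest helps but does not remove the drift.

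**The case against.** **Control 2 checks for drift.** It follows a pause of the same length as Phase 2, and continued settling makes T3 lower than T2, the opposite of a music effect. A reader might infer that the design as a whole is biased towards music. The documents do not support that: the bias towards music arises in Phase 1 versus Phase 2 and in comparisons with T0. What remains is that VI-3 does not use this protection for HR and BP, so a fall from T1 to T2 could be reported alone.

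**T0 is described as resting.** It is taken on the chair after calm preparatory steps. A reader might infer that T0 and T1 are known to be raised. The documents neither show nor exclude this; an unstated duration is not evidence of no rest.

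**The SAP names no decisive HR/BP comparison.** It would be wrong to say that it makes T1 versus T2 the test of music, or T0 the reference for all changes. T0 is one of four ANOVA levels.

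**The pauses may be recovery periods.** No drilling precedes Phase 1, so there is nothing to recover from. Residual arousal from Control 1 could also raise T2 and work against music. Both points are fair, and they leave the net direction uncertain. They do not make the run-ins equal.

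**The illustration is wide.** A range of 1% to 98% reflects the assumptions, covers HR only, and cannot say what happened in this study. That is conceded.

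**Conclusion.** The point holds in a limited form. T1 is the only drilling measurement without a timed run-in, so the Phase 1 to Phase 2 change in HR, SBP and DBP can mix settling with music. Control 2 partly guards against this, but the SAP does not require it to be used for these outcomes.

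The size is unknown. In the middle case the bias is 1.8 bpm, with about 7% false findings towards music against 0.4% nominal. These figures rest on the assumed settling curve, SD, reading times and alpha, and on no leftover arousal from drilling. The stronger reading, that settling has been counted as a music effect, is not supported.

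This is an inexpensive improvement that should be made. It affects the interpretation of secondary outcomes.

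**What to change.** **V-2, before step 4.** Add a 120 s seated rest on the chair without music, take T0 at its end, and start Phase 1 directly after. This costs about two minutes per patient and one line of text. It equalises the length of the run-in only: the music starts in the step 6 pause, and order and prior drilling still differ between phases.

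**VI-3, HR, SBP and DBP.** Pre-specify that a music effect requires T2 to be lower than both T1 and T3. Alternatively, test T2 against the mean of T1 and T3, which cancels linear drift and reduces curved drift. The first rule is the stricter: continued settling, or any effect of music that outlasts the pause, would lower T3 and make a finding harder to reach. Either costs a sentence.

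**If data collection is complete.** V reports the study in the past tense, from October 1 to December 23, 2025, so the added rest may be possible only in a further study. VI-4 still puts the analysis in the future. In that case:

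- apply the contrast rule to any data not yet analysed;
- report the rest before T0 and the T0 to T1 interval actually used, or say that they were not recorded;
- state the unequal run-in as a limitation.

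### The pain analysis in VI-3 has no place for a patient with an incomplete session; if patients stopped after Phase 1 because of high T1 pain, the complete-case music effect could be understated (minor)

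*Combined protocol and SAP*

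**What the plan says.** Section VI-3 gives the primary pain analysis as "Compare pain levels across phases using repeated measures ANOVA", with Friedman if normality fails, followed by "Post-hoc pairwise comparisons between phases (Phase 1 vs Phase 2, Phase 2 vs Phase 3) using Bonferroni adjustment". HR, systolic BP and diastolic BP get the same ANOVA over four phases. Pain is scored three times, at T1, T2 and T3 (V-2, steps 5, 7 and 9).

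The setting is drilling "performed without local anesthesia or in conditions where pharmacological analgesia is partially or totally ineffective" (section IV), and the first bout is "30 seconds of drilling without music" (V-2, step 5). The design is a "Single-arm, within-subject experimental study" (VI-1) "with a significant sample of 30 Lebanese adults" (section I).

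The document gives no analysis set, missing-data method, allowance for loss, or rule for recording a phase that is cut short. It does not say in words that incomplete patients are excluded; that follows from the named methods.

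**The concern.** Classical repeated measures ANOVA and Friedman need a full row per patient. If a patient provides T1 and then stops, the analyst must either discard the T1 score or fill in the missing values, and the plan covers neither.

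This matters because Phase 1 is the first painful bout and the one without music. A patient who stops after it has a recorded T1 score, and a high score is a plausible reason for stopping. Removing patients for a high T1 lowers the mean of T1 among those left by more than it lowers the mean of T2, so the T1–T2 difference shrinks. With 30 patients and no stated power calculation, a few such losses would be visible in the result.

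**Working it through.** **Inputs.** From the documents: n = 30; three pain scores; two Bonferroni contrasts. Not in the documents and therefore assumed: overall two-sided alpha 0.05 (0.025 per contrast), correlation between phases ρ = 0.5, number of patients lost, and effect size. The effect is the one that gives 80% power at n = 30 for a paired t-test at 0.025, which is 0.589 SDs of the difference. With ρ = 0.5 the SD of the difference is √(2(1 − 0.5)) = 1 SD, so the effect is also 0.589 in units of the VAS SD. The sample size of 30 cannot be reproduced, because none of its inputs is given.

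**1. Does the method need complete patients?** A standard Python repeated measures ANOVA routine (AnovaRM in statsmodels), run on 30 patients with one value removed, stopped with the message that the data are unbalanced. The patient must be dropped or the value filled.

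**2. Size of the bias if the highest-T1 patients stop after Phase 1.** If a fraction f is removed from the top of T1, the mean T1 of those kept falls by φ(z)/(1 − f) SD, where z cuts off the upper fraction f. Mean T2 falls by ρ times that amount. The difference is therefore too small by (1 − ρ) × φ(z)/(1 − f).

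At f = 3/30, z = 1.28 and φ(z) = 0.1755: 0.5 × 0.1755/0.9 = 0.097 SD, leaving 0.589 − 0.097 = 0.49 SD. Simulation at n = 30 gives slightly smaller bias than this large-sample formula:

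| Lost (highest T1) | Complete-case estimate (SD) | Power | Power from smaller n alone | Available-data likelihood estimate (SD) |
|---|---|---|---|---|
| 0 | 0.59 | 80% | 80% | 0.59 |
| 1 | 0.55 | 74% | 78% | 0.59 |
| 3 | 0.50 | 62% | 75% | 0.59 |
| 6 | 0.42 | 42% | 69% | 0.59 |

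Separate runs gave 0.55 to 0.56 SD with 1 lost and 60% to 63% power with 3 lost. Most of the fall in power with 3 lost comes from the assumed selection on T1, not from the smaller sample. The standard error of the available-data estimate rises only from 0.182 to 0.193 SD with 3 lost.

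**3. Other reasons for loss.** A second simulation used VAS SD 2, ρ = 0.6, a true effect of 1.0 point and 3 of 30 lost:

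| Loss follows | Complete-case | Available-data |
|---|---|---|
| Stable pain level, constant effect | 1.00 | 1.13 |
| Stable pain level, effect grows with pain | 0.94 | 1.10 |
| Stable pain level, effect shrinks with pain | 1.05 | 1.16 |
| Observed T1 | 0.85 | 0.99 |
| T2 | 1.14 | 1.26 |

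The bias is absent, downward or upward depending on why patients leave. Keeping partial data corrects it only when loss depends on the observed T1.

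**4. Which mixed model?** A random intercept alone assumes equal correlations between phases. With no missing data and a nominal level of 2.5%, its Phase 1 vs 2 contrast rejected a true null in about 5.1% of trials when the correlations T1–T2, T1–T3 and T2–T3 were 0.3, 0.3 and 0.8. With 0.5, 0.7 and 0.5 the rate was about 3.5%. The paired t-test stayed at about 2.5% in both cases. With complete data an unstructured covariance gives the same contrast as the paired comparison, so it avoids this inflation.

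**The case against.** The strongest objection is that the loss is hypothetical. Pain is collected in one sitting of 3 × 30 s + 2 × 120 s = 330 s, about 5.5 minutes. The procedure is explained before consent, and dental treatment continues afterwards, so leaving the study need not spare the patient any drilling. Section IV adds that some patients prefer drilling pain to numbness. No figure for loss comes from the documents. All of this stands, and it keeps the point minor.

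A reader might infer that losing the patients with most pain would necessarily bias the result. The documents do not support that. Each patient is their own control, so bias arises only if loss is related to the T1–T2 change. Nor is every gap harmful: a patient missing only T3 can still enter the Phase 1 vs 2 contrast, although the plan does not say whether the contrasts use all available pairs.

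A reader might also infer that a mixed model is a general cure. It is not. When loss followed stable pain level or T2, the available-data estimate was further from the truth than the complete-case one in the second simulation. The existing plan also has protections (sphericity check, Greenhouse–Geisser, Friedman) that a random-intercept model would discard.

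These objections do not support leaving VI-3 as it is. Stopping after Phase 1 because of the recorded T1 score is a plausible route to loss in this schedule, and for that route the named method is the weaker one.

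**Conclusion.** The point holds in a conditional form and is minor. The named methods have no place for an incomplete patient, and the plan is silent on what to do with one. If patients stop because of a high observed T1, the complete-case music effect could be understated: by about 0.03 SD with 1 of 30 lost and 0.09 SD with 3 lost, with power falling from 80% to about 74% and 62%. These sizes rest on an assumed correlation of 0.5, a true effect of 0.59 SD, 0.025 per contrast and removal of exactly the highest T1 scores. With no loss there is nothing to correct. The documents do not show that any patient was lost, and they do not fix the direction of bias if some were.

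**What to change.** In VI-3, estimate the phase contrasts for pain, HR, systolic BP and diastolic BP from a repeated-measures mixed model fitted by REML to every available phase value. Use phase as fixed effect, an unstructured within-patient covariance (not a random intercept alone) and small-sample t-based degrees of freedom. Keep the Bonferroni adjustment. Keep the planned repeated measures ANOVA with Greenhouse–Geisser, or Friedman, on complete cases as a sensitivity analysis; a gap between the two results signals that the reason for loss matters. Report the number of patients contributing to each phase, with the reason for every gap, and say that neither analysis protects against loss driven by T2 or unobserved pain.

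Cost: SAP wording and a slightly more complex model. VI-4 names Python, whose usual mixed-model routine reports z-based p-values, so the t-based degrees of freedom need to be added. Section V describes the study as already conducted, so the change must be documented as made after the original SAP; the number of incomplete patients should by then be countable. With complete data the phase estimates do not change.

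### The primary pain analysis can be declared positive from time drift alone, because no rule says which phase comparisons, in which direction, establish a music effect

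*Combined protocol and SAP*

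**What the plan says.** Section VI-1 describes a "Single-arm, within-subject experimental study" with these phases: "Baseline (T0), Phase 1 (pre-music silence), Phase 2 (music), Phase 3 (post-music silence". The order is the same for everyone, and there is no concurrent control. Under V-2, pain is scored at T1, T2 and T3 only, with a 120 s rest between drilling periods; music starts in the first rest and stops before the second.

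The hypothesis in section I is directional: music "induces a significant decrease in perceived pain and patient anxiety".

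For the primary outcome, VI-3 says: "Compare pain levels across phases using repeated measures ANOVA (or Friedman test if data violate normality"), followed by "Post-hoc pairwise comparisons between phases (Phase 1 vs Phase 2, Phase 2 vs Phase 3) using Bonferroni adjustment to correct for multiple testing".

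The plan does not state the alpha, whether tests are one- or two-sided, which result confirms the hypothesis, or whether one favourable pair is enough. Phase 1 vs Phase 3 is not among the pain comparisons. The sample is given as "30 adults undergoing dental treatment for caries", with no effect size, SD or power behind it.

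**The concern.** With a fixed order and no control group, the return to silence at T3 is the only protection against time effects. Pain may fall from one drilling period to the next through habituation, or rise as drilling goes deeper. The omnibus test responds to any difference among the three phases, whatever its cause or direction. If pain is simply falling, T1 vs T2 looks like a music effect. If it is simply rising, T2 vs T3 does.

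Because the two pairs are adjusted as separate tests and no rule combines them, an analyst who follows the plan to the letter could report a positive primary result on one pair. Bonferroni adjustment limits chance findings across the two tests; it does nothing about drift.

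**Working it through.** The plan has no power calculation to reproduce, so the check looks at how the planned tests behave at n = 30.

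**Inputs.** From the documents: n = 30, three pain scores per patient, two pairwise tests with Bonferroni adjustment. Assumed, because the documents are silent: overall two-sided 5%, hence 2.5% per pair; normal errors with equal correlation between phases; no missing scores; within-patient SD s = 12 mm. Between-patient variation cancels.

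**Formulas.**
- Pair: SE = √(2s²/n) = √(288/30) = 3.10 mm.
- Contrast C = T2 - (T1+T3)/2: SE = √(1.5s²/n) = √(216/30) = 2.68 mm.
- Omnibus: noncentral F on 2 and 58 df, λ = n·Σ(μⱼ - μ̄)²/s².

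**No music effect, linear drift of d mm per phase.** Here Σ(μⱼ - μ̄)² = 2d².
- d = 5: λ = 30 × 50/144 = 10.4, omnibus 81%. Pair 5/3.10 = 1.61 SE, giving 24%.
- d = 8: λ = 30 × 128/144 = 26.7, omnibus over 99%. Pair 8/3.10 = 2.58 SE, giving 59%.
- C has mean zero under any linear drift, so it falsely favours music in 2.5% of trials.

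**False support for music, no true effect** (noncentral distributions and simulation; phase means in mm for T1, T2, T3):

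| Pattern | Omnibus plus at least one favourable pair | Both pairs significant and favourable | C significant and favourable |
|---|---|---|---|
| 0, -5, -10 | 24% | 0.1% or less | 2.5% |
| 0, -8, -16 | 59% | 0.1% or less | 2.5% |
| 0, -8, -8 (plateau) | 57% | about 1% | 30% |
| 0, -12, -12 (plateau) | 93% | about 1% | 58% |

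A rising drift mirrors the falling one, with T2 vs T3 as the misleading pair.

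**Power for a true 8 mm effect, no drift.** Without carry-over, C has mean -8, or 8/2.68 = 2.98 SE. If half the effect persists at T3, its mean is -8 + 4/2 = -6 (2.24 SE). If all of it persists, -8 + 8/2 = -4 (1.49 SE).

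| Carry-over into T3 | C | Omnibus plus at least one favourable pair |
|---|---|---|
| None | 82% | 72% |
| Half | 58% | 57% |
| Full | 30% | 57% |

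Without carry-over, the omnibus alone has 74% power (λ = 30 × 42.7/144 = 8.9), one pair 59%, and both pairs 43%.

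Full carry-over of an 8 mm effect and an 8 mm plateau with no effect give the same phase means (0, -8, -8), with T3-T1 = -8 in both. T3-T1 therefore cannot tell drift from carry-over.

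**Range of assumptions.** With drift of 0.25, 0.5 and 0.75 s per phase, the omnibus rejects in 38%, 93% and 99.9% of trials (Friedman 30%, 83%, 99%), and one pair falsely favours music in 9%, 35% and 70%. A 5 mm drift is 0.25 s if s is 20 mm and 0.5 s if s is 10 mm, so the false-favourable rate at 5 mm runs from 9% to 35% over those SDs. With autoregressive errors and 0.5 s drift, the omnibus rejects in 84%, and C stays at 5% two-sided.

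**The case against.** A reader might infer that the plan does not test the music hypothesis, or ignores the return to silence. The documents do not support that. T1 vs T2 and T2 vs T3 are the two legs of the reversal. Read together, with both required to be significant in favour of music, they reject linear drift almost completely and hold false positives to about 1% under the plateaus tried. An omnibus test that responds to any phase difference is ordinary when directed comparisons follow it. The 24% to 59% arises only if one favourable pair is taken as enough, and the plan prescribes neither reading.

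The contrast is no complete remedy either. Against the omnibus (74%) or the omnibus plus any favourable pair (72%), its 82% is a gain of 8 to 10 points. That gain is essentially gone at half carry-over and becomes a clear loss at full carry-over, and the 120 s rest is the only washout described. Under a plateau, C is much less protective than requiring both pairs to be significant (30% against about 1% at 8 mm).

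All of this stands. It narrows the point but does not remove it: the missing rule leaves a choice between a reading prone to drift and one short of power, and that choice could be made after seeing the results. In every drift pattern tried, C gave fewer false positives than the omnibus plus any favourable pair.

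**Conclusion.** The concern holds as a missing decision rule in a fixed-order design. It should be fixed, but it does not make the data unable to address the hypothesis.

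The sizes depend on assumed SD, drift and effect values. The direction does not: for any steady drift, the omnibus test and one of the two pairs move towards significance without a music effect, and C does not.

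Two further inferences are not supported. The documents contain no pain data, so nothing shows that drift of this size occurred. And adopting C would not make the design robust: it removes linear drift only, and it does not substitute for a randomised order or a concurrent control.

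**What to change.** In VI-3, for pain:

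1. Name C = T2 - (T1+T3)/2 as the single primary contrast, tested at two-sided 5%, with its estimate and 95% CI.
2. Report T2-T1, T2-T3 and T3-T1 with 95% CIs as supporting estimates.
3. Claim a music effect only if C is significant in favour of music and both T2-T1 and T2-T3 point the same way. This asks for direction, not significance, on each leg; it is a modest extra guard, because under a plateau T2-T3 is centred on zero and can fall on the favourable side by chance.
4. Make the omnibus ANOVA or Friedman test descriptive.
5. State the assumptions: linear drift and no carry-over into Phase 3. Say that T3-T1 cannot separate the two, and report the behaviour under plateau and carry-over shown above.

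The change needs wording and re-analysis of T1, T2 and T3, which are already collected; no extra patients or measurements. The cost lies in timing. The document is dated 16/07/2025, yet section V describes the study as conducted from October 1 to December 23, 2025. Unless the contrast was fixed before the data were seen, it must be labelled post hoc and reported beside the analysis as planned.
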